**Visit 4 (Day 42, Midpoint)**

- **Symptom assessment; questionnaires.**

- **Physical Examination**
- **Blood Collection:** Serum and cells will be used or banked for translational/mechanistic studies.
- **Stool Sample Collection:** Subject will be provided with a take-home stool collection kit to collect stool samples.
- **Review of concomitant medication use.**
- Subjects will be given enough study medication to last until next visit.

**Visit 5 (Day 84)**

- **Symptom assessment; questionnaires.**
- **Physical Examination**
- **Blood Collection:** Serum and cells will be used or banked for translational/mechanistic studies.
- **Stool Sample Collection:** Subject will be provided with a take-home stool collection kit to collect stool samples.
- **Review of concomitant medication use.**

**Visit 6 (Day 92, at home follow-up)**

- **Symptom assessment; questionnaires.**

Cara App

The app used for the study is called Cara. It is available to the general public via the standard Apple app store. It uses encrypted transmission via HTTPS to transmit data from individuals to a cloud. Their cloud is provided by Microsoft Azur. The app as well as the sponsor will have access to the data.

Questionnaires**Irritable Bowel Symptom Severity Scale (IBS-SSS)**

IBS Severity Scoring System (IBS-SSS) is a widely used questionnaire to assess the symptom severity. It measures abdominal pain intensity, abdominal pain frequency, abdominal distension, dissatisfaction with bowel habits, and influence of IBS on life in general ("life interference") during the preceding week on a 0-100 scale, with the total IBS-SSS score ranging between 0 and 500, with higher scores indicating more severe symptoms.

**IBS-Global Improvement Scale**

Study patients completed an IBS global improvement scale (GIS) at visits 1, 2, 3 and 4. A GIS responder was defined as a patient who recorded either moderately or substantially improved to the question: "Compared with the way you usually felt during the 3 months before you entered the study, are your IBS symptoms over the past 4 weeks substantially worse, moderately worse, slightly worse, no change, slightly improved, moderately improved, or substantially improved?" Improvement in bowel urgency and global symptoms were analyzed for all IBS-C or IBS-M patients.

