### B3. DESCRIPTION OF RESEARCH PROTOCOL

#### A. Study Design – Overview, Methods, Procedures

##### Study Design

This is a 1:1 randomized, double blind 12-week comparison of effects of SH-DS01 by Seed Health Inc. versus placebo, in a cohort of 100 women with IBS with constipation or IBS with mixed bowel habits. 50 IBS-C or IBS-M patients will receive the daily synbiotic for 12 weeks, while 50 IBS-C or IBS-M patients will receive the placebo.

- **Initial Screening Session (1 hour)** – The purpose of this screening is to determine if the subject meets the qualifications to participate in the research study. After the screening is complete they will be notified whether they meet qualification or not. If the subjects qualify they will be provided with the supplementation and instructions for future study appointments. Informed Consent: This will be explained by a member of the study staff in an individual setting. After it has been explained and all questions have been answered, the subject will be asked to sign the consent form.

- Brief Medical History Form: After completing this short survey, the medical history will be reviewed and either approval will be issued to continue with the study or exclusion from further participation.
- Physical Exam:
  - Measurement of Height, Weight: the subject will be asked to remove shoes and any items in pockets (i.e. loose change, wallet, watch, cell phone, etc.) prior to having height (stadiometer) and weight (digital scale) measured.
- Medical history and interval history to include current medications, recording of adverse events (including intercurrent illness and any new diagnoses).
- Other Vital Signs: Temperature, Heart Rate, Blood Pressure
- **Study Procedures for Qualified Participants:** If the subject meets the study requirements and is cleared for study enrollment they will be asked to complete the following tasks:
  - **Pre-supplement wash-out (1 week):** during which the participant is to stop taking probiotics or antibiotics, in order to eliminate any residual effects of the synbiotic intervention. During this period, subjects will be provided with a single blinded placebo. Participants who are judged to be “responders” will be excluded from further participation in the trial.

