**Visit 3 (Randomization)**

- **Vital Signs:** Weight, Heart Rate, Blood Pressure.
- **Symptom assessment; questionnaires.**
- **Physical Examination**
- **Blood Collection:** General laboratory tests such as complete blood count (CBC) will be performed for all study subjects prior to randomization to ensure the safe and appropriate treatment of subjects. Clinical laboratory tests will be overseen by the PI or a physician sub-investigator. Functional analysis of serum and cells will be measured to look at LPS-binding protein, C-reactive protein (CRP) and a cytokine panel. Serum and cells will be used or banked for translational/mechanistic studies.
- **Stool Sample Collection:** Subject will be provided with a take-home stool collection kit to collect stool samples.
- **Assess pill count:** If pill count from run-in indicates <80% adherence/compliance, subject will not be randomized
- **Randomization:** Subject will be randomized into double-blind portion of the study. Subjects will be given enough study medication to last until next visit.

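### As listed, the Global Improvement Scale is read once after randomisation, at Day 42, and not at the end of the 12-week treatment; its visit list and the Visit 5 entry must be reconciled

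*Combined protocol and SAP*

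**What the plan says.** The Study Design section describes the trial thus: "This is a 1:1 randomized, double blind 12-week comparison of effects". The IBS-Global Improvement Scale paragraph sets the schedule: "Study patients completed an IBS global improvement scale (GIS) at visits 1, 2, 3 and 4". It also sets the response rule: "A GIS responder was defined as a patient who recorded either moderately or substantially improved to the question". The question compares recent symptoms with the three months before study entry, over a four-week look-back: "are your IBS symptoms over the past 4 weeks substantially worse".

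The visit descriptions fix the timing. They are headed "Visit 3 (Randomization", "Visit 4 (Day 42, Midpoint", Visit 5 at Day 84, and "Visit 6 (Day 92, at home follow-up". Visits 2 to 6 all carry the same entry, "Symptom assessment; questionnaires", and none of them names an instrument.

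Under Statistical analysis, participants who drop out count as failures for later outcomes. No outcome is designated primary or secondary.

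**The concern.** A 12-week comparison would normally report response at week 12. The GIS is the one scale for which the protocol says what a responder is, yet its visit list stops at the halfway visit. Site staff who follow that list would not ask the question at Day 84, and an answer not collected then cannot be reliably recovered later.

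Two things would be lost for this scale. Response gained or lost in the second half of treatment would not be seen. The rule that counts dropouts as failures would also have nothing to act on for a participant who completes Visit 4 and leaves between Days 43 and 84, because no later GIS reading is scheduled.

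**Working it through.** There is no stated figure to reproduce, so the check sets the visit list against the visit calendar.

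**Inputs**
- GIS visits: 1, 2, 3 and 4 (IBS-Global Improvement Scale paragraph).
- Visit days: Visit 3 is randomisation, taken as the start of the day count; Visit 4 is Day 42; Visit 5 is Day 84; Visit 6 is Day 92 (visit headings).
- Treatment length: 12 weeks (Study Design).
- Look-back: 4 weeks, or 28 days (GIS question).

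**Step 1: end of treatment.** 12 × 7 = 84 days, so Visit 5 is the end of treatment. 42 / 84 = 0.5, which agrees with the midpoint label on Visit 4 and supports counting days from randomisation.

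**Step 2: listed readings after randomisation.** Visits 1, 2 and 3 come before or at randomisation. Only Visit 4 comes after it. Count after randomisation: 1. Count at Day 84: 0.

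**Step 3: period described.** A 28-day look-back from each visit covers:

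| Visit | Listed for GIS? | Days covered | On treatment | Off treatment |
|---|---|---|---|---|
| 4 (Day 42) | Yes | 15–42 | 28 | 0 |
| 5 (Day 84) | No | 57–84 | 28 | 0 |
| 6 (Day 92) | No | 65–92 | 20 | 8 |

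No listed reading covers any of Days 43 to 84.

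**Step 4: after adding Visit 5.** There are two readings after randomisation, and the later one describes the last four weeks of treatment. A Visit 6 reading alone would not replace it, because 8 of its 28 days fall after treatment has ended.

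The screening session is not labelled Visit 1. That it is Visit 1 is inferred from the numbering, and the count in Step 2 does not depend on it.

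**The case against.** The strongest reply is that Visit 5 already lists questionnaires and that the GIS is one of the questionnaires the protocol describes. The GIS paragraph is written in the past tense and mentions an analysis of bowel urgency that appears nowhere else. This suggests, as an inference, carried-over text whose visit list was never matched to this six-visit trial. On that reading a Day 84 GIS was always intended. The reply has force, and intent cannot be settled from the documents. It does not remove the problem: a general line that names no instrument does not override an explicit list, and if the GIS was intended at Visit 5, the two places conflict and need the same correction.

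A reader might go further in four ways that the documents do not support.

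- *That the trial loses its main responder endpoint.* Only the GIS has a responder definition, but no endpoint is ranked. The title puts metagenomic stability, gut barrier integrity and metabolic output first, and stool and blood are collected at Day 84.
- *That symptom response at Day 84 cannot be reported at all.* The Adequate Relief item is a yes/no question, so the dropout rule could be applied to it. It and the IBS-SSS could describe Day 84 if given under the general line. Both look back one week, and neither asks about global improvement against the pre-study period, so they do not supply GIS response.
- *That the share of treatment days covered measures the damage.* The Day 42 look-back covers 28 / 84 = 33% of treatment, but a Day 84 reading alone would also cover 33%. What matters is which part is missed.
- *That the early readings are useless and should go.* The wash-out paragraph excludes participants judged to be placebo responders without saying how they are judged. Early GIS readings may serve that purpose, though the documents do not say so.

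**Conclusion.** The point holds. On the only explicit schedule, there is one GIS reading after randomisation, at the midpoint, none at the end of treatment, and none that describes Days 43 to 84. This rests on two assumptions: that the specific visit list governs over the general questionnaire line, and that days are counted from randomisation. If the first is wrong, what remains is a conflict between the GIS paragraph and the Visit 5 entry that still has to be resolved.

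It should be fixed, but it is not shown to compromise the trial's main question, because the GIS is not ranked as a primary or secondary endpoint. The size of the problem is one missing end-of-treatment reading on one scale; no bias or loss of power can be derived from the documents.

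**What to change.** 1. Correct the visit list in the IBS-Global Improvement Scale paragraph to include Visit 5 (Day 84), and name the GIS in the Visit 5 entry so that the two agree. State whether it is also given at Visit 6.
2. State that GIS response by arm at Day 84 is the end-of-treatment GIS analysis, with Day 42 as supportive. This need not make the GIS a primary or secondary endpoint.
3. Keep the pre-randomisation readings unless the sponsor confirms that they are not used for the placebo-responder exclusion.

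The cost is a short text amendment and one added question at a visit that already has questionnaires. It should be in place before participants reach Day 84.

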**IBS-Adequate Relief Question**

The IBS-Adequate Relief (IBS-AR) is a dichotomous single item that asks participants "Over the past week have you had adequate relief of your IBS symptoms?". It serves as an additional way to assess GI symptoms in the IBS-C or IBS-M patient cohorts.

**Visceral Sensitivity Index**

The Visceral Sensitivity Index (VSI) is a self-reported survey measure that will be given to the IBS-C or IBS-M cohort for completion. It will assess gastrointestinal-specific anxiety, the cognitive, affective, and behavioral response to fear of gastrointestinal sensations, symptoms, and the context in which these visceral sensations and symptoms occur.

**SH-DS01 Capsules****Probiotics for Digestive Health/Oxidative Stress/GI Immunity:***Bifidobacterium breve SD-BR3-IT**Lactobacillus rhamnosus SD-LR6-IT**Lactobacillus plantarum SD-LP1-IT**Bifidobacterium longum SD-BB536-JP**Lactobacillus reuteri SD-LRE2-IT**Bifidobacterium infantis SD-M63-JP**Lactobacillus rhamnosus HRVD113-US**Bifidobacterium lactis HRVD574-US**Bifidobacterium breve HRVD521-US**Lactobacillus casei HRVD300-US**Bifidobacterium longum HRVD90b-US**Bifidobacterium lactis SD-BS5-IT**Bifidobacterium lactis SD150-BE**Lactobacillus rhamnosus SD-GG-BE**Lactobacillus reuteri RD830-FR***Probiotics for Women's Health:***Bifidobacterium adolescentis SD-BA5-IT**Lactobacillus crispatus SD-LCR01-IT**Lactobacillus salivarius SD-CRL1328-IT**Lactobacillus fermentum SD-LF8-IT***Probiotics for Dermatological Health:***Bifidobacterium longum SD-CECT7347-SP**Lactobacillus casei SD-CECT9104-SP**Bifidobacterium lactis SD-CECT8145-SP***Probiotics for Cardiovascular Health:***Lactobacillus plantarum SD-LDL400-UK**Bifidobacterium lactis SD-MB2409-IT***Prebiotics:**

Indian Pomegranate [whole fruit and skin] (*Punica granatum*)

**Prohibited Therapy During Study Period**

- Patient is currently using or has in the past used recreational or medicinal cannabis, or synthetic cannabinoid based medications (including Sativex®) or supplements (including hemp oil/extracts) within one month prior to study entry and is unwilling to abstain for the duration for the study.
- Patient has consumed any probiotic product three days prior to screening and/or is unwilling to abstain from consuming these during the study.
- Intake of antibiotics in the past 2 weeks (i.e. penicillin, amoxicillin, cephalexin (Keflex), erythromycin (E-Mycin), clarithromycin (Biaxin), azithromycin (Zithromax), ciprofloxacin (Cipro), levofloxacin (Levaquin), ofloxacin (Floxin), co-trimoxazole (Bactrim), trimethoprim (Proloprim), tetracycline (Sumycin or Panmycin), doxycycline (Vibramycin), gentamicin (Garamycin), or tobramycin (Tobrex). The supplement in the present study may have a minor interaction with these medications.

**B. Statistical Considerations****Statistical analysis**

This study is a randomized, double-blind, placebo-controlled trial comparing study subjects treated with a daily synbiotic vs. placebo. We will perform all statistical tests all under the null hypothesis that there is no difference between the two groups (synbiotic and placebo) against the two-sided alternative that they are not equivalent. Analyses will be conducted using an Intention to Treat (ITT) analysis and will include all study subjects who are randomized into this trial. Study subjects who drop out of the study will be considered failures for subsequent outcomes.

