## PART B STUDY DESCRIPTION

TITLE OF PROTOCOL	A randomized, double blind, placebo-controlled study to evaluate the impact of a multi-strain synbiotic on fecal metagenomic stability, gut barrier integrity, and metabolic output of the gut microbiota in premenopausal adult females.
Principal Investigator	[name]

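### The only missing-data rule counts dropouts as failures, but failure has a defined value only for the two binary outcomes; for IBS-SSS, VSI and the stool measures the analyst must choose one or drop women

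*Combined protocol and SAP*

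**What the plan says.** Section B3.B (Statistical Considerations) is a single paragraph. It defines the analysis set as intention to treat, which "will include all study subjects who are randomized into this trial", and tests the null hypothesis "against the two-sided alternative that they are not equivalent". Its one sentence on missing data is "Study subjects who drop out of the study will be considered failures for subsequent outcomes". It does not define failure, name a test or model, describe imputation or a sensitivity analysis, or say what happens when a woman misses a visit without leaving.

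The outcomes are described elsewhere. Two are binary in section B3.A: the GIS responder (moderately or substantially improved) and the IBS-Adequate Relief item (yes or no). IBS-SSS is a score, "with the total IBS-SSS score ranging between 0 and 500, with higher scores indicating more severe symptoms". VSI is a questionnaire score. The protocol title names "fecal metagenomic stability, gut barrier integrity, and metabolic output of the gut microbiota" as what the trial evaluates, and stool is collected around Visits 3, 4 and 5. None of these non-binary measures has a responder threshold. The IBS-SSS value of 150 in section B3.C is an entry criterion, not a definition of response.

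**The concern.** The rule is written for all subsequent outcomes, yet *failure* is a category and most of the measures are quantities. For IBS-SSS or VSI, the analyst would have to pick a number to stand for failure or dichotomise at a threshold that the plan does not give. For a metagenomic measure there is not even a natural worst value. The remaining option is to leave the woman out of that analysis, which contradicts the intention-to-treat sentence immediately before the rule.

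Two things are at stake. First, a failure value far from the observed scores inflates the variance and costs power. Second, if dropout differs between arms, the comparison partly becomes one of dropout rates, and a difference can appear without any treatment effect. Since nothing in the document fixes the value in advance, two competent analysts could follow the plan and report different results.

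**Working it through.** **Inputs from the documents.** 50 women per arm, 1:1, 12 weeks (Study Design); two-sided tests (B3.B); IBS-SSS maximum 500 (Questionnaires).

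**Inputs not in the documents, so assumed.** Alpha 0.05; week-12 IBS-SSS SD 80-100; placebo mean 200-300; dropout 5-20%, unrelated to the outcome; the failure value itself.

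**The plan's own figure.** The total of 100 comes with no effect size, SD, power or dropout allowance, so it cannot be reproduced. Solving backwards, 50 per arm has 80% power at a standardised difference of (1.960 + 0.842) × √(2/50) = 0.56. This is used below as the true effect (50.4 points at SD 90).

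**Step 1: failure scored as a fixed value w, dropout d.** In each arm with mean μ:

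- mean = (1 − d)μ + d·w
- variance = (1 − d)SD² + d(1 − d)(w − μ)²

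With SD 90, placebo mean 250, active mean 199.6, w = 500 and d = 10% in both arms:

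- difference = 0.9 × 50.4 = 45.4
- placebo variance = 7,290 + 0.09 × 250² = 12,915
- active variance = 7,290 + 0.09 × 300.4² = 15,412
- standard error = √((12,915 + 15,412)/50) = 23.8
- power = Φ(45.4/23.8 − 1.960) = 48%

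Observed cases only, 45 per arm: Φ(0.56 × √22.5 − 1.960) = 76%. For 20% dropout, 40 per arm: 71%.

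| IBS-SSS, equal dropout | 10% | 20% |
|---|---|---|
| Observed data only | 76% | 71% |
| Failure = 500, SD 90, mean 250 | 48% | 31% |
| Failure = 500, SD 80, mean 200 (lowest) | 37% | 23% |
| Failure = 500, SD 100, mean 300 (highest) | 58% | 42% |

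Simulation at SD 90 and mean 250 agrees for the t test (47% and 31%). A rank test loses less (57% and 40%).

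**Step 2: a milder value.** Suppose failure means no improvement, so each dropout keeps her baseline (assumed mean 280, SD 70), with placebo mean 220, active mean 169.6 and SD 90. At 10% dropout:

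- placebo variance = 7,290 + 0.1 × 4,900 + 0.09 × 60² = 8,104
- active variance = 7,290 + 490 + 0.09 × 110.4² = 8,877
- standard error = √((8,104 + 8,877)/50) = 18.4
- power = Φ(45.4/18.4 − 1.960) = 69%

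At 20% dropout the same steps give 58%.

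**Step 3: unequal dropout, no true effect.** The false difference is (0.15 − 0.05)(w − μ). With mean 220 and SD 90:

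| Failure value | False difference | Standard error | Type I error |
|---|---|---|---|
| 270 | 5 points | 17.3 | about 6% |
| 300 | 8 points | 17.7 | about 7% |
| 500 | 28 points | 23.8 | about 21% |

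For a true benefit of 50.4 (mean 250, w = 500) and 15% dropout on the synbiotic against 5% on placebo, the estimate is (0.95 × 250 + 25) − (0.85 × 199.6 + 75) = 17.8. With the imbalance reversed it is (0.85 × 250 + 75) − (0.95 × 199.6 + 25) = 72.9.

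**Step 4: binary outcomes.** With assumed response of 58% versus 30%, power is 81.5% with no dropout. Counting dropouts as non-responders gives 74% at 10% dropout and 65% at 20%, against 77% and 72% for observed cases. The rule costs little more there than the dropout itself.

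**The case against.** The strongest reply is that the plan never proposes a worst score. A reader might infer from the word failure that dropouts will be set to 500 on IBS-SSS, but 500 appears only as the top of the scale. Failure is the language of responder analysis. It fits GIS and IBS-AR directly, and it could mean no improvement or worst rank elsewhere, or could be applied after dichotomising IBS-SSS. This stands: the defect is an undefined value, not a stated worst-score imputation, and the lower power figures belong to one reading only.

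A reader might also infer that the rule biases every comparison. With equal dropout unrelated to outcome and a common failure value, it only shrinks the effect by the factor (1 − dropout rate). A false difference needs unequal dropout. The documents give no dropout rates. Section B5 lists gastrointestinal side effects of the synbiotic, which makes imbalance possible but does not show it.

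It is tempting to add LPS-binding protein, CRP and cytokines to the affected outcomes. They are named only at Visit 3, at randomisation; later visits mention only serum and cells to be used or banked. The documents do not establish them as post-randomisation outcomes, so the point does not rest on them.

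Finally, no primary outcome is named, so it is unknown whether the rule governs a binary or a continuous primary. That limits what can be said about the trial's main result. It does not remove the gap for the scores and stool measures.

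**Conclusion.** The concern holds in this form: the sole missing-data rule can be applied as written to GIS responder and IBS-AR, and cannot be applied to IBS-SSS, VSI or the stool measures without a definition that the plan lacks. The consequence ranges from modest to serious depending on the value chosen. At 10% equal dropout, power is about 69% under a no-improvement value and 37-58% under 500, against 76% from observed data. At 20% the figures are about 58%, 23-42% and 71%. With 5% versus 15% dropout and no effect, type I error runs from about 6% to about 21%. All of this rests on assumed SDs, means, dropout rates and alpha, and on dropout unrelated to outcome. The lack of a definition does not depend on those assumptions.

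**What to change.** Restrict the failure rule, worded as non-response, to GIS responder and IBS-AR. State what counts as dropping out and how a single missed visit is handled.

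For continuous outcomes, analyse all randomised women with a likelihood-based repeated-measures model that has the Visit 3, Day 42 and Day 84 values in the response vector, with baseline means constrained equal across arms, or use multiple imputation. Placing Visit 3 only as a covariate would not do: women who leave before Day 42 would then contribute no response and fall out of the analysis.

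Add one missing-not-at-random sensitivity analysis, either reference-based imputation or a tipping point. Keep collecting the scheduled questionnaires and samples from women who stop capsules but stay in the study. Fix the wording before unblinding.

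The cost is a revised paragraph and a little more analysis work; the visit schedule is unchanged. The main analysis would rely on a missing-at-random assumption, which the sensitivity analysis is there to test.
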